1.1 Objectives, Endpoints, and Estimands

Objectives and endpoints are listed in Table 1-1.

Table 1-1: Objectives and Endpoints

Objectives	Endpoints
Primary	
To explore the efficacy of elinzanetant on sleep disturbances associated with menopause as determined by PSG	Primary endpoint Change from baseline in WASO at week 4 as measured by PSG Secondary endpoints Change from baseline in WASO at Week 12 as measured by PSG Change from baseline in SE at week 4 as measured by PSG Change from baseline in SE at week 12 as measured by PSG Change from baseline in SE at week 12 as measured by PSG Exploratory endpoints Change from baseline at week 4 and week 12 in PSG measures of sleep onset, duration, and continuity: LPS, TST, SOL, SOLN1, WTDS, EMWT, TWT, NAW, mean duration of awakenings, WASO each quarter of the night Change from baseline at week 4 and week 12 in PSG measures of different sleep stage durations: time and percent in stage N1 sleep, time and percent in stage N2 sleep, time and percent in non-REM sleep, time and percent in REM sleep, REM onset latency from sleep onset Change from baseline at week 4 and week 12 in other PSG measures: arousal index
	and number of stage shifts
Secondary	
To explore the efficacy of elinzanetant on sleep disturbance associated with menopause as determined by patient reported outcomes	Change from baseline in PROMIS SD SF 8b total score at week 4 Change from baseline in PROMIS SD SF 8b total score at week 4 Change from baseline in PROMIS SD SF 8b total score at week 12 Change from baseline in ISI total score at week 4 Change from baseline in ISI total score at week 12 Exploratory endpoints Change from baseline in subject-reported measures (as determined by the sleep diary (SD)) of sleep onset, duration, and continuity over time: sWASO, sLPS, sTST, sTIB, sSE, sNAW Change from baseline in proportion of days with participants rating "quite a bit" or "very much" sleep disturbance due to HF as measured by HFDD over time

rsion 2.0 Page: 11 of 57

To evaluate the safety of elinzanetant for the treatment of sleep disturbances associated with menopause	TEAEs Abnormal laboratory parameters
To explore the relationship between HFs and sleep disturbance as determined by PSG To explore the efficacy of elinzanetant on the frequency of anxiety symptoms To evaluate the efficacy of elinzanetant on the PGI-S and PGI-C	Frequency of HFs as measured by HFDD over time WASO as measured by PSG over time Change from baseline in GAD-7 total score over time Actual values of the PGI-C individual item scores over time Change from baseline in PGI-S individual item scores over time
Other pre-specified	item scores over time
To evaluate variability in exposure in relation to the efficacy and safety for elinzanetant	Systemic exposure of elinzanetant in plasma via sparse PK sampling
To further investigate the study intervention and similar compounds (e.g., mode-of- action-related effects, safety) and to further investigate pathomechanisms deemed relevant to sleep disturbances associated with menopause.	Various biomarkers (e.g., diagnostic, safety, pharmacodynamic, monitoring, or potentially predictive biomarkers)
To investigate the efficacy of elinzanetant on sleep disturbance associated with menopause determined by Sleepiz One+	Parameters captured remotely and continuously at home by Sleepiz One+including but not limited to e.g., WASO, TST, SE

Version 2.0 Page: 12 of 57

Estimands

The primary clinical question of interest for the primary objective is:

Does elinzanetant improve sleep disturbances associated with menopause? Specifically, what is the difference in mean change from baseline in WASO as measured by PSG at week 4 comparing elinzanetant to placebo in women with sleep disturbances associated with menopause assuming no study treatment interruption and discontinuation and no use of prohibited concomitant medications impacting sleep?

The attributes of the main estimand for the primary endpoint are as follows:

- Population: Women aged 40–65 with sleep disturbances associated with the menopause, further defined by the key inclusion/exclusion criteria.
- Variable: Change from baseline in WASO as measured by PSG at week 4.
- Treatment: Elinzanetant 120 mg or placebo.
- ICEs and strategies: Important ICEs to consider are listed in Table 1-2. (See Section 6.4 for details regarding identification of ICEs).

Table 1-2: Primary Estimand: ICEs and Strategies to Address Them

ICEs	Proposed Strategy	Data Handling Method	Interpretation
Temporary study treatment interruption ^a	Hypothetical	Discard data collected during the ICE	The treatment effect that would be if participants did not have any temporary treatment interruptions
Premature discontinuation of study treatment	Hypothetical	Discard data collected after the ICE	The treatment effect that would be if participants did not discontinue the randomized treatment
Intake of prohibited concomitant medication having impact on efficacy	Hypothetical	Discard data collected during the ICE	The treatment effect that would be if participants did not take prohibited concomitant medications impacting sleep

^a Definition of temporary study treatment interruption:

Week 4 = Treatment taken <80% during day 1 to the last PSG night at week 4 (inclusive) OR treatment taken on <5 days during the last 7 days up to the last PSG night at week 4 (inclusive).

• Population level summary: Mean change from baseline in WASO as measured by PSG at week 4.

Version 2.0 Page: 13 of 57

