6.1 Study Intervention(s) Administered

Table 6-1: Study Interventions

Arm name	Elinzanetant	Placebo	
Intervention Name	BAY 3427080 / elinzanetant	Placebo	
Type	Drug	N/A	
Dose Formulation	Soft gel capsule	Soft gel capsule	
Unit Dose Strength(s)	60 mg	N/A	
Dosage Level(s)	Two capsules daily (120 mg)	Two capsules daily	
Route of Administration	Oral	Oral	
Use	Experimental	Placebo	
Packaging and Labeling	Study Intervention will be provided in an Alu-Alu blister with 12		
	soft gel capsules. 5 blisters will be placed into 1 box containing capsules for treatment of one month. Each box will be labeled as		
	required per country requireme	nt.	
Current name	BAY 3427080	N/A	
Former Name	NT-814		

Alu = Aluminium; N/A = Not applicable.

Study intervention will be dispensed at the study visits summarized in the SoA and the first dose should be taken at home in the evening on the same day. In general, study treatment will be taken once daily before going to sleep with or without food.

If a participant forgets to take a dose in the evening, then the dose can be taken at any time up to 2 AM the same night. After this time, the dose should not be taken and will be considered a missed dose.

Returned study intervention may not be re-dispensed to a different participant.

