7.1.3 Temporary Discontinuation

In the event that a participant experiences an AE which the investigator believes is treatment related and which the participant finds intolerable, a break in dosing of up to one week is permitted. If, on reintroduction of the study medication, the AE recurs and remains intolerable, the study intervention will be permanently withdrawn. A break in dosing will not result in extension of the overall dosing period.

Temporary discontinuation is also allowed in the following 2 cases:

- Temporary discontinuation of study intervention for an intercurrent illness, at the discretion of the investigator.
- In the event of a trial-continuity issue (e.g. caused by a pandemic), the Sponsor may provide additional guidance in study-specific communication.

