4.5.1 Extent of Exposure

Treatment duration will be defined as the number of days from the day of first study intervention intake up to and including the day of last study intervention intake and will be summarized using descriptive statistics by study treatment. Treatment duration will be presented based on the data collected via the eCRF. If the date for end of exposure is not available in eCRF, the last day of intervention intake from eDiary will be used to determine the end of exposure.

The compliance (as percentage) will be calculated as:

100 * Number of capsules taken / Number of planned capsules

The number of planned tablets is calculated as:

Treatment duration * 2

All capsules, including the placebo capsules, will be counted. For participants who withdraw prematurely from the study treatment, compliance will be calculated up to the time of last dose. The compliance will be summarized descriptively by study treatment. In addition, percent of compliance will be categorized into 3 groups, <80%, 80 to 120% >120%, and the categories will be summarized by study treatment.

Version 2.0 Page: 35 of 57

Compliance will be calculated and presented twice, once based on the ePRO daily instrument 'Study medication intake documentation' and once based on the eCRF 'Drug Accountability' and 'Study Intervention' pages. If the 'Study medication intake documentation' on the second PSG night at week 12/EoT is missing but the last treatment intake on the eCRF 'Study intervention' pages indicate that the participant took treatment on the night, the 'Number of study medication capsules taken' on the 'Study medication intake documentation' will be imputed with 1 capsule.

The summaries for treatment duration and compliance will be presented for the overall intervention period, (i.e., 12 weeks).

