6.4.2 Temporary treatment interruption

Temporary treatment interruption is defined as

- Treatment taken < 80% during day 1 to the last PSG night at week 4 (inclusive) OR treatment taken on < 5 days during the last 7 days up to the last PSG night at week 4 (inclusive) for week 4.
- Treatment taken < 80% during day 1 to the last PSG night at week 12 (inclusive) OR treatment taken on < 5 days during the last 7 days up to the last PSG night at week 12 (inclusive) for week 12.

If the week 4 PSG assessment is missing, day 30 will be used instead of the last PSG night in the definition of treatment interruption for week 4 only for participants who have not prematurely discontinue treatment prior to day 30. Similarly for week 12, day 86 will be used only for participants who have not prematurely discontinue treatment prior to day 86.

The criterion for treatment taken on 5/7 days during the corresponding week prior to and including the last PSG night, as defined above, is met, if treatment has been taken for less than 5 days (i.e., at least 3 missed intakes). To calculate the number of days per week with treatment intake, a day where at least one capsule was taken, will be considered as a day with treatment intake.

To identify whether < 80% treatment was taken, compliance up to and including the last PSG night at week 4 will be calculated as

100 * Number of capsules taken up to and including the last PSG night at week 4 / (2 * study duration up to and including the last PSG night at week 4)

Compliance up to and including the last PSG night at week 12 will be calculated as

100 * Number of capsules taken up to and including the last PSG night at week 12 / (2 * study duration up to and including the last PSG night at week 12)

Study duration up to and including the last PSG night at week 4 and week 12 is derived as the number of days from the day of first study intervention intake up to and including the last PSG night at week 4 and week 12 respectively. The number of capsules taken up to and including the last PSG night at week 4 and week 12 will be calculated based on the ePRO instrument 'Study medication intake documentation'. If the 'Study medication intake documentation' on the second PSG night at week 12/EoT is missing but the last treatment intake on the eCRF 'Study intervention' pages indicate that the participant took treatment on

Version 2.0 Page: 54 of 57

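### The under-80% part of the treatment-interruption rule sums capsules with no nightly limit, so recorded extra capsules can offset a gap before the last week (low priority)

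*SAP*

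**What the plan says.** SAP 1.1 (Table 1-2, footnote a) defines temporary interruption at Week 4 by two tests joined by OR. The first is a capsule share: "Week 4 = Treatment taken <80% during day 1 to the last PSG night at week 4 (inclusive"). The second is a day count: "treatment taken on <5 days during the last 7 days up to the last PSG night at week 4 (inclusive"). The footnote gives no formula; it is in SAP 6.4.2.

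- **Capsule share:** "100 * Number of capsules taken up to and including the last PSG night at week 4 / (2 * study duration" to that night). The count comes from the participant's daily diary entry. No ceiling per night is stated. Week 12 uses the same formula.
- **Day count:** "a day where at least one capsule was taken, will be considered as a day with treatment intake". A day counts once, however many capsules are entered.
- **Planned dosing** (Protocol 6.1): "Two capsules daily (120 mg").
- **Consequence** (SAP 4.2.2.1): data within the interruption timeframe are left out of the primary MMRM, and a PSG night without treatment is dropped.
- **Compliance reporting** (SAP 4.5.1): "percent of compliance will be categorized into 3 groups, <80%, 80 to 120% >120"%. This is presented once from the diary and once from the eCRF.

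SAP 4.8 records that the day-count test was moved from Weeks 3 and 4 in the protocol to the seven days up to the last PSG night.

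**The concern.** The estimand asks what the effect would be with no treatment interruption, so the flag should turn on whether treatment was interrupted. An uncapped capsule sum does not quite do that, because two extra capsules recorded on any night cancel one missed night. Two women with the same gap can therefore be classified differently only because one of them entered more than two capsules on some nights.

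The day-count test cannot be offset in this way, but it looks only at the last seven days. Since the change noted in SAP 4.8, a gap before that week depends on the capsule share alone. At stake is whether an affected woman's Week 4 WASO enters the primary model, and likewise her Week 12 value for the secondary endpoint.

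**Working it through.** **Scale of the design.** The plan's precision figure reproduces. With SD 33.2 and 35 per arm, t(0.95, 68) x 33.2 x sqrt(2/35) = 13.23. Multiplying by sqrt(chi-square(0.90, 68)/68) gives 14.65 minutes, against 14.7 stated in SAP 5. This point does not affect it; it serves only as a yardstick under the objection.

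**Inputs.** Two capsules per night (Protocol 6.1). Flag if 100 x capsules/(2 x days) is below 80, or if there are fewer than 5 intake days in the last 7 (SAP 6.4.2). Day 30 is the second night of a visit starting on day 29, and also the SAP's default when the PSG is missing: "day 30 will be used instead of the last PSG night in the definition of treatment interruption for week 4".

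**Week 4, last PSG night on day 30.** Planned capsules are 2 x 30 = 60, and the pass mark is 0.80 x 60 = 48. With k missed nights and e extra capsules, the woman passes if 2(30 - k) + e is at least 48, that is, if e is at least 2k - 12.

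| Diary | As written | Intake days in last 7 | Flag as written | At most 2 per night |
|---|---|---|---|---|
| 6 missed (nights 10-15), no extras | 48/60 = 80.0% | 7 | No | 80.0%, no flag |
| 7 missed (nights 10-16), no extras | 46/60 = 76.7% | 7 | Yes | 76.7%, flag |
| Same 7 missed, one 4-capsule night | 48/60 = 80.0% | 7 | **No** | 76.7%, flag |
| 10 missed (nights 8-17), four 4-capsule nights | 48/60 = 80.0% | 7 | **No** | 66.7%, flag |
| 7 missed (nights 23-29), 4 extra capsules | 50/60 = 83.3% | 1 | Yes | 76.7%, flag |
| 3 missed (nights 25-27), 6 extra capsules | 60/60 = 100% | 4 | Yes | 54/60 = 90.0%, flag |

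The two rows in bold are the loophole. The last two rows show that the day-count test closes it near the PSG: extras cannot hide three or more missed nights in the final seven.

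**Later visits.** The visit window is day 29 plus 7 days (Protocol 1.3), so the last PSG night can fall on days 30 to 37. Seven missed nights with no extras give:

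- day 34: 54/68 = 79.4%, flagged
- day 35: 56/70 = 80.0%, not flagged
- day 36: 58/72 = 80.6%, not flagged
- day 37: 60/74 = 81.1%, not flagged

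On days 35 to 37 a one-week gap passes because of the 80% threshold itself. On day 37, eight missed nights give 58/74 = 78.4%, and two extra capsules bring this to 60/74 = 81.1%.

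**Week 12, day 86.** Planned capsules are 172, and the threshold is 0.80 x 172 = 137.6. Eighteen missed nights give 136/172 = 79.1%, flagged. Two extra capsules give 138/172 = 80.2%, not flagged on this test.

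**The case against.** The strongest reply is that the mechanism needs conduct outside the protocol. Protocol 6.1 treats a dose not taken by 2 AM as missed and describes no make-up dosing. Protocol 6.5 has diary entries checked against capsule counts and dosing deviations recorded. This stands: nothing shows that diary entries above two occur.

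A reader might take the over-120% class in SAP 4.5.1 as evidence that they do. It is weaker than that. The class applies to diary-based compliance as well as to drug accountability, so totals above plan are provided for. In the accountability version, however, they can arise from unreturned capsules, which Protocol 6.5 counts as taken.

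A reader might also treat seven nights as the longest break allowed. Protocol 7.1.3 does say "a break in dosing of up to one week is permitted", but for an intolerable adverse event judged treatment-related; breaks for intercurrent illness carry no stated limit. Seven nights is used here only as an example.

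There are partial safeguards. SAP 4.1.3 has intercurrent events reviewed before unblinding, and the first supplementary estimand (SAP 4.2.3.1) keeps interruption data under treatment policy. Neither removes the offset from the primary rule, since no stated criterion tells the blinded review to discount extra capsules.

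Finally, any effect is likely to be small. As an illustration only, assume one retained Week 4 value is wrong by half to one SD (16.6 to 33.2 minutes). In an arm of 35 the raw mean then moves by 16.6/35 = 0.47 to 33.2/35 = 0.95 minutes, against a planned half width of 14.7.

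**Conclusion.** The capsule-share test is uncapped as written, and recorded extra capsules can turn a flagged gap into an unflagged one. Two extra capsules are enough for a seven-night gap when the last PSG night is day 30, and for 18 missed nights at day 86. This requires both a gap with fewer than three missed nights in the last seven and at least one night recorded above two capsules. The examples assume complete diaries with full dosing on all other nights.

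A reader might infer that women with real gaps generally stay in the primary analysis for this reason, or that the Week 4 estimate is biased. The documents support neither. The frequency of entries above two is not given and may be zero, so the bias cannot be computed; each affected woman would be 1/78 = 1.3% of those randomised. Nor are all women with the same gap and no extras removed: six missed nights of 30 pass on the threshold alone, as do seven when the last PSG night is on days 35 to 37. This is a low-priority improvement that aligns the flag with the estimand, not a demonstrated bias.

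**What to change.** In SAP 6.4.2, for both Week 4 and Week 12, define the numerator of the under-80% test as the sum over nights of min(capsules recorded that night, 2). One-capsule nights still count as half, and the day-count test is unchanged. Leave the exposure compliance in SAP 4.5.1 uncapped so that intake above plan stays visible there.

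The cost is one line of text and one of code before unblinding. If the blinded diaries show no night above two, no result changes. Otherwise a few more PSG visits may be classed as interrupted. An entry that really covers two nights would be undercounted, so entries above two should be listed and resolved at the blinded review of intercurrent events.

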1.2 Study Design

This is a multi-center, multi-country, double-blind, randomized, parallel-group, placebo-controlled, pilot intervention study in women with sleep disturbances associated with the menopause.

Figure 1-1: Study Schema

ICF = signing of informed consent form.

The study duration will be about 23 weeks (plus potential washout period), including:

Screening: After giving informed consent, participants will be withdrawn from prohibited concomitant medications at SCR-1 visit if needed. Screening period consists of 3 visits.

Randomization: At the end of the screening period, the participants will be randomized into elinzanetant and placebo arms in a 1:1 ratio. Randomization will be stratified by the average weekly frequency of moderate to severe HFs (including nighttime HFs) over the 14 days prior to the respective eligibility check (<35 moderate to severe HFs per week, ≥35 –<50 moderate to severe HFs per week).

Intervention period: Intervention period will last about 12 weeks:

• 120 mg (2x 60 mg soft gel capsules) of elinzanetant or matching placebo orally once daily for 12 weeks

Follow-up: The intervention period will be followed by a 4-week safety follow-up period.

The visit frequency will be once every 1–2 weeks during the screening period (depending on the scheduling of PSG) and once every 4–5 weeks during the intervention and follow-up periods.

The study includes 3 stationary visits in a sleep laboratory. Each of these visits encompasses 2 consecutive nights. This results in a total of 6 nights in the sleep laboratory.

Primary analysis will be performed after database release after LPLV.

Version 2.0 Page: 14 of 57

2. Statistical Hypothesis

The primary objective for the study is to estimate the treatment effect of elinzanetant compared to placebo in the change from baseline in WASO at week 4 as measured by PSG. No hypotheses are planned to be tested.

2.1 Multiplicity Adjustment

Not applicable.

3. Analysis Sets

For the purposes of analysis, the following analysis sets are defined in Table 3-1:

Table 3-1: Definition of the Analysis Sets

Participant Analysis Set	Description	
Enrolled	All participants who signed the informed consent form.	
Full Analysis Set (FAS)	All participants randomly assigned to study treatment.	
Safety Analysis Set (SAF)	All participants randomly assigned to study treatment who were exposed to study treatment at least once.	
Sleepiz One+ Analysis Set (SLAS)	All participants who provided consent for use of medical device and randomly assigned to study treatment with at least 1 non-missing Sleepiz One+ evaluation.	

The FAS will be used to analyze endpoints related to the efficacy objectives and participants will be analyzed according to their randomized study treatment.

The SAF will be used to analyze the endpoints and assessments related to safety and participants will be analyzed according to the study treatment received.

The SLAS will be used to analyze the sleep endpoints assessed via the Sleepiz One+ device and participants will be analyzed according to their randomized study treatment.

Final decisions regarding the assignment of participants to analysis sets will be made during the review of study data and documented in the final list of important deviations, validity findings and assignment to analysis set(s).

Version 2.0 Page: 15 of 57

4. Statistical Analyses

4.1 General Considerations

The statistical evaluation will be performed by using the software SAS (release 9.4 or higher; SAS Institute Inc., Cary, NC, USA) and/or R (version 3.5.2 or higher; R Foundation for Statistical Computing, Vienna, Austria).

All variables will be summarized using descriptive statistics as appropriate by study treatment. Continuous variables will be summarized using at least the following descriptive statistics: number of non-missing observations and missing data, arithmetic mean, std dev, median, minimum, and maximum. The geometric mean, geometric std dev and CV will be provided instead of the arithmetic mean and std dev for variables where lognormal distributions are assumed. Categorical data will be summarized with frequency tables with the number of observations and percentages. Confidence intervals (CI) will be 2 sided with a confidence level of 95% for descriptive statistics and 90% level from the MMRM. Treatment differences will be provided for elinzanetant vs placebo.

Variables recorded in the electronic case report form (eCRF) and relevant derived variables will be shown in data listings, whereby only randomized participants will be included. Data from screening failures will only be shown in the 'Screening failure' listing.

Number of decimal places for summary statistics will be the following:

Table 4-1: Number of Decimal Places for Summary Statistics

Statistic	Number of decimal places
Minimum, maximum	Same as original data
Mean, median, std dev	1 more than in original data
Frequencies (%)	1 digit

